# **11. ORGANISATION: STUDY MANAGEMENT AND OVERSIGHT ARRANGEMENTS**

# 11.1. Study management

Overall management of the study will be the responsibility of the joint chief investigators, [name], based at Queen's University Belfast and [name], University of Aberdeen.

A clinical trials co-ordinator at the Centre for Experimental Medicine at Queen's University Belfast will lead the governance support for the project.

The main study office is in the Centre for Healthcare Randomised Trials (CHaRT) based within the Health Services Research Unit, University of Aberdeen and provides day to day support for the clinical centres. The study manager in CHaRT at Aberdeen will take responsibility for the day to day transaction of study activities. The data co-ordinator will provide clerical and support for data queries to the study.

The EDNA Study Office Team will meet formally at least monthly during the course of the study to ensure smooth running and trouble-shooting. Finally, we intend to produce a yearly EDNA Study Newsletter for participants and collaborators to inform everyone of progress and maintain enthusiasm.

# **11.2.** Local organisation in sites

The local principal investigator (PI) and research nurse will be responsible for all aspects of local organisation including identifying and consenting participants along with facilitating the delivery of the study and notification of any problem or unexpected developments for the duration of the study. The research nurse will be responsible for ensuring that study data is collected for baseline assessments, collecting and recording participant study data on study specific case report forms and will log details onto the remote web-based data capture system.

# 11.3. Project Management Group (PMG)

The study is supervised by a Project management Group (PMG). This consists of the grant holders and representatives from the Study Team. Observers may be invited to attend at the discretion of the PMG. The PMG will meet/teleconference monthly on average.

The research team has the expertise to cover the clinical and surgical aspects of the research.

# 11.4. Steering Committee (SC)

The study is overseen by a Steering Committee (SC). The membership of this Committee is comprised of at least four independent members along with the Chief Investigator ([name]) or a nominated delegate. The study sponsor, other EDNA grant-holders and key members of the central office (e.g. the study manager) can participate in SC meetings but are not members. The funders will be notified in advance of meetings and a representative invited to attend. Other relevant experts may be invited to attend as appropriate. Details of the membership of the SC can be found at the start of this protocol. CHaRT recommends to

steering committees that they adopt the MRC CTU template to form the basis for each individual study charter. The SC will meet approximately yearly throughout the study.

# 11.5. Data Monitoring Committee (DMC)

There will be no DMC for this study as there is no blinding or interventional aspect to the study.

# **11.6.** Patient and public involvement

We have collaborated with the Macular Society and the Royal National Institute of Blind People (RNIB). They assisted with the development of the protocol, patient information leaflets, consent forms and will help monitor study progress including accrual and engagement at the local level. At least one representative of the Macular Society will be a member of the steering committee.

# **12. RESEARCH GOVERNANCE, DATA PROTECTION AND SPONSORSHIP**

# **12.1.** Sponsorship and Research Governance

Queen's University Belfast is the sponsor for the study.

The study will be co-ordinated under the auspices of CHaRT based at HSRU, University of Aberdeen, with support from University of Oxford, Moorfields Eye Hospital NHS Foundation Trust and Royal Liverpool and Broadgreen University Hospitals NHS Trust. This will ensure compliance with Research Governance, and provide centralised study administration, database support and economic and statistical analyses. CHaRT is a registered Clinical Trials Unit with particular expertise in running multicentre RCTs of complex and surgical interventions.

The CI will ensure, through the steering committee, that adequate systems are in place for monitoring the quality of the study (compliance with appropriate governance) and appropriate expedited and routine reports, to a level appropriate to the risk assessment of the study.

# 12.2. Data protection

Data collected during the course of the research will be kept strictly confidential and accessed only by members of the study team. Participant's details will be stored on a secure database under the guidelines of the 1998 Data Protection Act and regular checks and monitoring are in place to ensure compliance. Data are stored securely in accordance with the Act and archived to a secure data storage facility. The CHaRT senior IT manager (in collaboration with the Chief Investigator) will manage access rights to the data set. Participants will be allocated an individual specific study number and their details will be anonymised on the secure database. We anticipate that anonymised study data may be shared with other researchers to enable international prospective meta-analyses. To comply with the 5th Principle of the Data Protection Act 1998, personal data will not be kept for longer than is required for the purpose for which it has been acquired.

# **13. ETHICS AND REGULATORY APPROVALS**

The Office for Research Ethics Committees in Northern Ireland (ORECNI) has reviewed this study. The study will be conducted according to the principles of good clinical practice provided by Research Governance Guidelines. Annual progress reports and a final report at the conclusion of the study will be submitted to ORECNI REC within the timelines defined in the regulations.

#### **14. QUALITY ASSURANCE**

The study will be monitored to ensure that the study is being conducted as per protocol, adhering to Research Governance, and the appropriate regulations.

#### 14.1. Risk assessment

An independent risk assessment has been carried out by the sponsor. The approach to, and extent of, monitoring is specified in the study monitoring plan and is appropriate to the risk assessment of the study.

#### **15. FINANCE AND INSURANCE**

The study is funded by a grant awarded by the NIHR Health Technology Assessment programme.

The necessary study insurance is provided by Queen's University Belfast.

#### **16. END OF STUDY**

The end of follow-up for each participant is defined as the final data capture to answer the research question. The end of the study is defined as the end of funding.

The end of the study will be reported to the REC within 90 days, or 15 days if the study is terminated prematurely. The Investigators will inform participants and ensure that the appropriate follow up is arranged for all involved.

A summary report of the study will be provided to the REC within one year of the end of the study. An end of study report will also be issued to the funders at the end of funding.

# **17. DATA HANDLING, RECORD KEEPING AND ARCHIVING**

Clinical data will be entered into the database by the local investigator and/or research nurse working in each hospital site, together with data from questionnaires completed at clinic. Staff in the study office will work closely with local research nurses to ensure that the data are as complete and accurate as possible. Extensive range and consistency checks will further enhance the quality of the data.

The sponsor is responsible for ensuring that study data is archived appropriately. Essential data shall be retained for a period of at least 10 years following close of the study.

#### **18. SATELLITE STUDIES**

It is recognised, that the value of the study may be enhanced by smaller ancillary studies of specific aspects. Plans for these will be discussed in advanced with the Project Management Group. REC approval will be sought for any new proposal, if appropriate.

#### **19. AUTHORSHIP PUBLICATION**

We have a commitment to publish the findings of the research. At a minimum this study will have a results paper published in a peer- reviewed medical/scientific journal. If all grant-holders and researcher staff fulfil authorship rules, group authorship will be used under the

collective title of 'the EDNA study Group'. If one or more individuals have made a significant contribution above and beyond other group members but where all group members fulfil authorship rules, authorship will be attributed to the named individual(s) and the EDNA Study Group.

For reports which specifically arise from the study but where all members do not fulfil authorship rules (for example, specialist sub-study publications), authorship should be attributed to the named individual(s) for the EDNA Study Group.

To safeguard the integrity of the main study, reports of explanatory or satellite studies will not be submitted for publication without prior arrangement from the Project Management Group.

We intend to maintain interest in the study by publication of EDNA newsletters at intervals for staff and collaborators. Once the main report has been published, a lay summary of the findings will be sent in a final EDNA Newsletter to all involved in the study. Further details on the publication policy can be found in Appendix A.

#### Appendix A: Authorship Policy

# 1. PRINCIPLES OF AUTHORSHIP

The following principles of authorship have been derived from editorial publications from leading journals (see references) and are in accordance with the rules of the international Committee of Medical Journal Editors.

#### a. Group authorship

Group authorship will be appropriate for some publications, such as main reports. This will apply when the intellectual work underpinning a publication 'has been carried out by a group, and no one person can be identified as having substantially greater responsibility for its contents than others'. In such cases the authorship will be presented by the collective title - The EDNA Study Group - and the article should carry a footnote of the names of the people (and their institutions) represented by the corporate title. In some situations one or more authors may take responsibility for drafting the paper but all group members qualify as members; in this case, this should be recognised using the by-line 'Jane Doe *and* the Study Group'. Group authorship may also be appropriate for publications where one or more authors take responsibility for a group, in which case the other group members are not authors but may be listed in the acknowledgement (the by-line would read 'Jane Doe *for* the Study Group').

#### b. Individual authorship

Other papers, such as describing satellite studies, will have individual authorship. In order to qualify for authorship an individual must fulfil the following criteria:

i. each author should have participated sufficiently in the work represented by the article to take public responsibility for the content.

- ii. participation must include three steps:
  - conception or design of the work represented by the article OR analysis and interpretation of the data OR both; AND
  - drafting the article or revising it for critically important content; AND
  - final approval of the version to be published.

Participation solely in the collection of data is insufficient by itself. Those contributors who do not justify authorship may be acknowledged and their contribution described.

#### c. Determining authorship

Tentative decisions on authorship should be made as soon as possible. These should be justified to, and agreed by, the Project Management Group. Any difficulties or disagreements will be resolved by the Steering Committee.

# 2. AUTHORSHIP FOR PUBLICATION ARISING FROM EDNA

#### a. Operationalising authorship rules

We envisage two types of report (including conference presentations) arising from the EDNA study and its associated projects:

i. Reports of work arising from the main EDNA study

If all grant-holders and research staff fulfil authorship rules, group authorship should be used under the collective title of 'The EDNA Study Group'; if one or more individuals have made a significant contribution above and beyond other group members but where all group members fulfil authorship rules, authorship will be attributed to 'Jane Doe and the EDNA Study Group'. ii. Reports of satellite studies and subsidiary projects

Authorship should be guided by the authorship rules outlined in Section 1 above. Grant-holders and research staff not directly associated with the specific project should only be included as authors if they fulfil the authorship rules. Grant-holders and research staff who have made a contribution to the project but do not fulfil authorship rules should be recognised in the Acknowledgement section. The role of the EDNA Study Group in the development and support of the project should be recognised in the Acknowledgement section. The lead researcher should be responsible for ratifying authorship with the Project Management Group.

For reports which specifically arise from the EDNA study but where all members do not fulfil authorship rules (for example, specialist sub-study publications), authorship should be attributed to 'Jane Doe for the EDNA Study Group'. If individual members of the group are dissatisfied by a decision, they can appeal to the Management Group for reconciliation. If this cannot be achieved, the matter should be referred to the Steering Group.

#### b. Quality assurance

Ensuring quality assurance is essential to the good name of the study group. For reports of individual projects, internal peer review among members of the Project Management Group is a requirement prior to submission of papers. All reports of work arising from the EDNA study including conference abstracts should be peer reviewed by the Project Management Group.

The internal peer review for reports of work arising from the EDNA project is mandatory and submission may be delayed or vetoed if there are serious concerns about the scientific quality of the report. The Project Management Group will be responsible for decisions about submission following internal peer review. If individual members of the group are dissatisfied by decisions, the matter may be referred to the Steering Group.

The Project Management Group undertakes to respond to submission of articles for peer review at the Project Management Group Meeting following submission (assuming the report is submitted to the study secretariat in Aberdeen at least two weeks prior to the meeting).

## **Introduction**

### **Background and rationale**

Neovascular age-related macular degeneration (nAMD) causes severe visual loss and is the most common cause of blindness in persons > 50 years old in the western world (Royal College of Ophthalmologists guidelines 2009). In recent years, there have been major advances in the clinical management of patients with nAMD, notably the introduction of anti VEGF treatments. When active nAMD is confirmed, treatment with anti VEGF therapy is initiated ([name] 2010, IVAN investigators 2012; Martin 2012). In the early phases of treatment (i.e. up to about one year), at each subsequent visit which is usually on an 8 week cycle, patients are re-assessed to evaluate disease activity. Thus there is an opportunity to obtain information on unaffected fellow eyes of patients with nAMD in one eye.

Approximately 8-10% of patients with nAMD in one eye will develop the same condition in the fellow eye per year. Detection of nAMD at a stage when damage to the retina is not permanent with prompt initiation of treatment could result in much better preservation of sight. Therefore there is a clear need for an easily and rapidly performed cost effective monitoring test that will detect the onset of nAMD with high diagnostic accuracy.

Managing neovascular AMD presents an enormous burden to the NHS. Ophthalmology accounts for 10% (five million per year) of all outpatient attendances to the NHS, and age-related macular degeneration accounts for 15% of all ophthalmology outpatient attendances. (Age-related macular degeneration guidelines 2009 Royal College of Ophthalmologists).

Scrutiny of the outcomes from the large clinical trials shows that if treatment is commenced when acuity is better than 73 letters (Snellen equivalent 6/12), over 90% maintain this level of vision or better (Martin 2012, IVAN 2012). Better acuity is associated with smaller nAMD lesions and thus early detection of nAMD and prompt initiation of treatment will result in final visual outcomes that are consistent with good visual function. The proposed research is particularly important because (1) there is a large patient pool whose care pathway requires regular visits and monitoring (every 8 weeks) offering the ideal situation for a study of early detection of nAMD in fellow eyes of patients with nAMD in one eye (2) these patients are subjected to tests of function (acuity) and tomography and it is current clinical practice to acquire information on both eyes at every visit (3) the tomographic examination is quick (performed without the need for pupillary dilation and the quality of the tomograms are high as all the NHS units offering anti VEGF therapies have invested in high resolution Fourier domain OCT technology (4) the patients are motivated and the NOD has shown that attendance is high with dropout less than 10% per annum.

## **Interventions**

The interventions (index tests) to be evaluated are:

1. Fundus evaluation: a positive fundus evaluation is one as determined by an expert showing signs of nAMD on the fundus.
2. Visual acuity using the early treatment diabetic retinopathy study chart (ETDRS): a positive test is one where there is a reduction of 10 letters or more in best corrected visual acuity (BCVA).
3. Amsler test: a positive Amsler test is, as assessed by the clinician, appearance of a new area of distortion or blank spots when previously there was none or clear evidence of increase in the area of distortion or scotoma.
4. Optical coherence tomography (OCT): a positive test is abnormal findings indicative of nAMD as interpreted by an experienced ophthalmologist, specifically it is a positive answer to any of the following: SRF on OCT, neovascular PED on OCT, IRF on OCT or any other reason for OCT being positive.
5. Patient's subjective assessment of vision: the patient is asked "how is your vision in the unaffected eye?" The patient is prompted to answer one of the following four possibilities "about the same or better", "a bit worse", "worse" or "much worse". A positive test is one where the patient reports "much worse".

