# Definition of test positive:

A positive visual acuity test is one where there is a reduction of 10 or more letters in BCVA from baseline and this will trigger a reference standard test (FFA). In the event that the triggered FFA is negative, and at subsequent visits there is additional vision loss, an FFA can be triggered at the discretion of the clinician.

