# 3.2.4. Amsler test

The Amsler chart or grid is a grid of horizontal and vertical lines used to monitor a person's central visual field. It is a simple, inexpensive, diagnostic tool that aids the detection of visual disturbances caused by changes in the retina, particularly the macula (e.g. macular degeneration). In the test, after covering one eye the person looks with the eye to be tested fixating at the small dot in the centre of the grid printed on the Amsler test sheet. Patients with macular fluid may see distortion of the straight lines or areas of the pattern may be missing. Patients should have a normal Amsler test in the study eye at baseline. In patients who have distortion on Amsler at baseline, Amsler tests will not be collected in the subsequent assessments or trigger any FFA.

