# Definition of test positive:

For the purpose of this study a positive Amsler test is, as assessed by the clinician, appearance of a new area of distortion or blank spots when previously there was none or clear evidence of increase in the area of distortion or scotoma. This will trigger a reference standard test (FFA).

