When abnormalities as a consequence of AMD develop in the retinal and choroidal circulations (such as dilation of existing vessels or growth of new vessels), there is accumulation of fluid within the macular tissue compartments with separation of the normal tissue interfaces. In addition seepage of haemoglobin, other cellular and proteinaceous or lipid constituents of blood into the retina can cause alterations in the internal reflectivity and homogeneity of the retinal layers and these can take the form of areas of dense hyperreflective material or foci. The appearance of abnormalities when previously there was none as well as their spatial localisation and distribution can alert the clinician to the onset of nAMD even when the signs are subtle and only just discernible.

For the purpose of this study any OCT machine can be used for data collection.

Definition of test positive:

Any of the above positive findings in the OCT exam as interpreted by an experienced ophthalmologist, will trigger a reference standard test (FFA)

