### **Definition of valid follow-up period**

If a participant is included as defined above, then the valid follow-up period will be from baseline until the date of the last valid FFA (as defined above).

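### The A1 window opens at baseline and OCT and fundus positives need not be new, so a finding already cleared by the diagnostic FFA can count in the primary analysis

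*SAP*

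**What the plan says.** **OCT rule.** SAP, Interventions, item 4 begins with a judgement: "a positive test is abnormal findings indicative of nAMD as interpreted by an experienced ophthalmologist". It then makes this operational: "specifically it is a positive answer to any of the following: SRF on OCT, neovascular PED on OCT, IRF on OCT". A catch-all item for other grounds completes the list. There is no condition that the finding was absent earlier. Item 1 (fundus evaluation) likewise asks only whether an expert sees signs of nAMD.

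**Protocol on OCT.** The narrative in section 3.2.5 says that "The appearance of abnormalities when previously there was none" can alert the clinician. The formal definition of a positive test that follows does not carry this over as a condition. Protocol section 8 lets the SAP prevail where the two differ.

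**Window and collapse.** Under the SAP's Definition of valid follow-up period, "the valid follow-up period will be from baseline until the date of the last valid FFA". The next section makes any positive in that period an overall positive. Table 2 then scores the person as a true or false positive according to the FFA.

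**The other tests.** SAP item 3 requires for Amsler "appearance of a new area of distortion or blank spots when previously there was none or clear evidence of increase" in the defect. Protocol 3.2.4 adds: "In patients who have distortion on Amsler at baseline, Amsler tests will not be collected in the subsequent assessments or trigger any FFA". Acuity is positive on "a reduction of 10 or more letters in BCVA from baseline" (protocol 3.2.3), and SAP sensitivity analysis 4 re-bases acuity after a false positive confirmed by FFA.

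**The concern.** The study asks how well each test detects the onset of nAMD during monitoring. The diagnostic FFA at entry has already shown that the study eye is free of nAMD, and both Table 1 in the protocol and Table 1 in the SAP record index tests at recruitment. If the baseline OCT or fundus result lies inside the A1 window, a positive call at that point is fixed for the whole of follow-up. It becomes a false positive if the eye never converts. If the eye converts, up to three years later, the same baseline call becomes a true positive although it detected nothing.

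The authors dealt with pre-existing abnormality for Amsler, by dropping the test when distortion is present at baseline, and for acuity, by measuring from baseline and re-basing in a sensitivity analysis. OCT and fundus have neither protection. The A1 McNemar comparisons of OCT or fundus with acuity or Amsler would therefore set tests that can be positive on entry against tests defined by change. The error would lower OCT and fundus specificity and slightly raise their sensitivity.

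**Working it through.** **1. The plan's own figure.** Inputs from the SAP, Sample size: two-sided 5%, 90% power, sensitivity 80% against 65% (d = 0.15), disagreement ψ = 0.30, incidence 28%, loss 12%.

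Converters needed = [1.96·√ψ + 1.2816·√(ψ − d²)]² / d² = [1.96·√0.30 + 1.2816·√0.2775]² / 0.0225 = 135.9, so 136. Then 136 / 0.28 = 486, against the stated 491 (1% apart), and 491 / 0.88 = 558 against the stated 560. The planning figures reproduce, and this point disputes none of them. With 491 analysed there are 491 × 0.28 = 137.5 converters and 491 × 0.72 = 353.5 non-converters.

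**2. Path of a static finding through A1.**
- The diagnostic FFA is negative in the study eye and the baseline OCT is called positive.
- The window opens at baseline, so the result is inside it.
- Any positive makes the person OCT-positive.
- If every later FFA is negative, Table 2 gives a false positive. If a later FFA is positive, it gives a true positive.

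A second route does not need the baseline scan. If the same unchanged finding is called positive again at a follow-up visit, the person is positive through that visit. Moving the start of the window closes the first route only.

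**3. Size.** Let b be the share of eyes with a static finding that is called positive. The documents give no value, so b is an assumption. Assume too that static findings are independent of other OCT results, and that the planning values of 94% and 80% do not already include them. Then:
- specificity = 0.94 × (1 − b), a loss of 0.94 points per 1% of eyes;
- sensitivity = 0.80 + 0.20 × b, a gain of 0.20 points per 1% of eyes;
- extra false positives = 353.5 × 0.94 × b.

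| b (assumed) | OCT specificity | extra false positives | OCT sensitivity |
|---|---|---|---|
| 0 | 94.0% | 0 | 80.0% |
| 1% | 93.1% | 3 | 80.2% |
| 2% | 92.1% | 7 | 80.4% |
| 5% | 89.3% | 17 | 81.0% |
| 10% | 84.6% | 33 | 82.0% |

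**4. Effect on a McNemar comparison.** Suppose OCT and acuity both truly have 94% specificity, with independent false positives and 354 non-converters. Put f₁ = 1 − 0.94(1 − b) and f₂ = 0.06. The discordant cells are f₁(1 − f₂) and (1 − f₁)f₂. Under the normal approximation, the chance that OCT is declared the less specific test is 2.5% at b = 0, 7% at 1%, 16% at 2%, 30% at 3% and 62% at 5%. So the effect is minor at 1% and serious by 5%.

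**The case against.** **Expert reading.** The OCT rule is not a tally of features. The ophthalmologist must judge the findings indicative of nAMD, and the listed detachment is a neovascular one. A reader might infer that any recorded fluid or PED makes an eye positive; the text does not say that. A clinician may well discount a known, stable finding that FFA has cleared. This stands, but nothing tells clinicians to do so, and practice could differ between sites.

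**Do such eyes exist?** Entry requires an unaffected study eye and excludes both nAMD at baseline and confounding retinal pathology. A reader might take the early and late nAMD rows for OCT in the dummy baseline table as proof that such eyes are enrolled. They are blank template rows in tables that the SAP calls illustrative, and the fundus rows also include an exudative category that entry excludes. The ELM and EZ disruption listed in Appendix 1 is not a named OCT-positive item. So the share may be small.

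**Does the baseline scan count?** The SAP speaks elsewhere of collapsing repeated monitoring assessments and of index results during follow-up, which suggests that it does not. The sentence that defines the window nevertheless says from baseline, and Table 2 refers to all available prior time points. The wording leaves both readings open.

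**As-called scoring is defensible.** An OCT called positive at a monitoring visit triggers an FFA. If that FFA is negative, this is a real false positive with a real burden. The objection is sound for monitoring visits, and it is why A1 should keep the call as made. It does not cover a baseline result that precedes monitoring.

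**Other analyses.** A2 and A3 drop positives confined to early visits in eyes followed for longer, but not a finding that persists. Sensitivity analysis 1 uses reading-centre OCT, again without a newness rule.

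**Conclusion.** The gap in the wording is real and lies in the primary analysis. As written, A1 can count an OCT or fundus positive that predates monitoring and that the diagnostic FFA had already cleared, and no planned analysis isolates new findings for these two tests.

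The direction is clear: lower OCT and fundus specificity and marginally higher sensitivity. The size is about 0.94 points of OCT specificity per 1% of affected eyes, given independence and a 94% that excludes static findings. That figure comes from a pilot OCT study, and the documents do not say whether it already contains such findings. If it does, the calculation overstates the loss.

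Two stronger readings are not supported. A reader might infer that the rule could create the trial's whole 7-point specificity contrast. That needs 1 − 0.87/0.94 = 7.4% of eyes, a value obtained by solving for the gap and not found in either document. A reader might also infer that the primary OCT definition is wrong and must become a change rule. As-called scoring at monitoring visits is a legitimate choice, and replacing it would evaluate a different test from the one that prompted FFA. The documents support a correction to the window, one added sensitivity analysis and a reported count.

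**What to change.** 1. In the SAP, in the definitions of the valid follow-up period and of the index test result for analysis A, state that only index tests done after the baseline assessment count in A1. This is a wording change and a date filter.
2. Keep the as-called OCT and fundus definitions in A1. Add a pre-specified sensitivity analysis, parallel to sensitivity analysis 4 for acuity, in which OCT and fundus are positive only for a listed finding not recorded at baseline or at the last FFA-negative visit.
3. Report how many eyes had a positive OCT or fundus result at baseline, so that the share b is known rather than assumed.

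The cost is one extra analysis and one table row. Item 2 depends on item-level OCT answers (SRF, neovascular PED, IRF, other) being held for baseline. The documents show baseline OCT being collected but not at what level of detail, so this should be checked first. FFA triggering and patient care are unaffected.
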